Study: 221AD304 Version: 2.0

Clarification Statement

Due to the discontinuation of the Aducanumab program and the early termination of the study,

[figure not shown]
Also, to reduce participant burden, the clinical efficacy assessments will be removed, leaving only safety assessments.

2. Follow-up/End of Study (FU/EOS) Visit: assessments and timing (Section 4.2, Table 3)

Version 4 of the current protocol mandates that participants return for a Follow-up/End of Study visit (also referred to as the safety follow-up visit) 18 weeks after the participant's last dose at 152 weeks (see Section 4.2, Table 3, Schedule of Activities).

Clarification Statement

Due to the discontinuation of the Aducanumab program and the early termination of the study, all participants will be asked to complete their Follow-up/End of Study Visit 12 weeks (+/– 5 days) after the participant's last dose of study treatment. In addition, similar to the End of Treatment Visit, the number of assessments that need to be completed is now reduced to lessen participant burden. These assessments are reported below in Table 2. If a participant has had their last dose of study treatment and it has been more than 12 weeks since their last dose and the participant has not had their safety follow-up, then they should complete a safety follow-up within the next 30 days, as defined in Table 2.

Study: 221AD304 Version: 2.0

Table 2 Revised Schedule of Assessments for the End of Treatment and Follow-up Visits

Study Assessments	Week 154/End of Treatment Visit (within 2 weeks of last dose)	Follow up/End of Study Visit (12 weeks after last dose +/- 5 days)
Body Weight	X	
Hematology, Blood Chemistry, and Urinalysis	X	
Alzheimer's Disease Status	No longer being completed	
Physical Examination	X	X
Neurological Examination	X	X
Vital Signs	X	X
12-Lead Paper ECG	X	
ADA	X	
Aducanumab Serum Concentration	X	

Study: 221AD304 Version: 2.0

Study Assessments	Week 154/End of Treatment Visit (within 2 weeks of last dose)	Follow up/End of Study Visit (12 weeks after last dose +/- 5 days)	
C-SSRS	X	X This will now be completed	
Brain MRI		X	
AE Reporting	Monitor and record continuously throughout the study		
Concomitant Therapy and Procedures	Monitor and record continuously throughout the study		
SAE Reporting	Monitor and record continuously throughout the study		

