3.3. Study Treatment Periods

• Core period

For subjects who received at least one dose of study treatment in LTE visits, core period is from the first dose of treatment in the study to before the first dose date in LTE period. For subjects who did not receive any dose in any LTE visits, core treatment period is from the first dose in study to the very last date of any assessment done as completed in RAVE or in any vendor database.

• Long-term extension period

Study: 221AD304 Version: 2.0

Long-term extension period, also called LTE period, is from the first dose date in LTE treatment period to the very last date of any assessment done as completed in RAVE or in any vendor database.

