5.7. Safety Endpoints

5.7.1. General Considerations

The primary estimand employs the treatment-policy strategy to evaluate the safety of BIIB037 determined by the following 4 attributes:

- Population: Intended population for BIIB037 defined through the study inclusion/exclusion criteria. All subjects in the safety population will be used in analyzing this estimand
- Variable: adverse events

Product: Aducanumab
Study: 221AD304
Statistical Analysis Plan
Version: 2.0

• Handling intercurrent events: regardless of intercurrent events including treatment discontinuation and use of concomitant therapies

• Population-level summary: incidence of adverse events

The Safety population will be used for safety analyses of AEs, clinical laboratory data, Columbia Suicide Severity Rating Scale (C-SSRS) data, ECG data and vital sign data (all the safety data except for ARIA data). Safety MRI population will be used for analyses of ARIA data.

In general, AEs will be summarized based on incidence and incidence proportion. Incidence is defined as the number of subjects who experienced an event. Incidence proportion (%) is defined as the number of subjects who experienced an event divided by the total number of subjects in the analysis population, i.e., percentage. Each subject will be counted only once within each category.

All AEs will be coded using the MedDRA dictionary (version 26.1).

When analyzing data for the core period or LTE period, an event will be assigned to one period by the start date. The event duration will be based on the start date and the end date of that event.

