5.7.5.2. Qualitative analyses

For qualitative analyses, all values will be included (not just the "analyzed record" within each visit window in the quantitative analyses).

Shift analyses

Laboratory data will be summarized using shift tables where appropriate. Each subject's hematology, blood chemistry and urinalysis numeric values will be flagged as "low", "normal", or "high" relative to the normal ranges of the central laboratory or as "unknown" if no result is available. Each subject's urinalysis categorical values will be flagged as "positive" or "negative", or "unknown" if no value is available.

Shifts from 221AD304 baseline to high/low status will be presented for hematology, blood chemistry and urinalysis numeric parameters, and shifts from 221AD304 baseline to abnormal (positive) will be presented for urinalysis categorical parameters. Shift to low includes normal to low, high to low, and unknown to low; Shift to high includes normal to high, low to high, and unknown to high. Subjects need to have at least one post-baseline evaluation and a baseline value not low or high or positive (including missing) to be included in the analysis.

Study: 221AD304 **Version:** 2.0

Potentially Clinically Significant laboratory abnormalities analyses

For hematology, blood chemistry and urinalysis, the number of subjects with potentially clinically significant laboratory abnormalities post-baseline will be summarized for the parameters provided in Table 8. Subjects need to have at least one post-baseline evaluation in the active treatment period and a baseline value not potentially clinically significant (including missing) to be included in the analysis.

Table 8 Criteria to Determine Potentially Clinically Significant (PCS) Laboratory
Abnormalities

Clinical Laboratory Abnormality Criteria		
Parameter name	PCS Low	PCS High
HEMATOLOGY		
White blood cells	<3.0 x 109/L	>16 x 109/L
Lymphocytes	<0.8 x 109/L	>12 x 109/L
Neutrophils	<1.5 x 109/L	>13.5 x 109/L
Monocytes	N/A	>2.5 x 109/L
Eosinophils	N/A	>1.6 x 109/L
Basophils	N/A	>1.6 x 109/L
Red blood cells	≤3.5 x 1012/L	≥6.4 x 1012/L
Hemoglobin - Females	≤95 g/L	≥175 g/L
Hemoglobin - Males	≤115 g/L	≥190 g/L
Hematocrit - Females	≤32%	≥54%
Hematocrit - Males	≤37%	≥60%
Platelet count	≤75 x 109/L	≥700 x 109/L
BLOOD CHEMISTRY		
Alanine aminotransferase (ALT)	N/A	>3 x ULN
Aspartate aminotransferase (AST)	N/A	>3 x ULN
Alkaline phosphatase (ALP)	N/A	>3 x ULN
Total bilirubin	N/A	>1.5 x ULN

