Blood urea nitrogen (BUN)	N/A	≥10.7 mmol/L
Creatinine	N/A	≥176.8 umol/L
Sodium	≤126 mmol/L	≥156 mmol/L

Study: 221AD304 Version: 2.0

Clinical Laboratory Abnormality Criteria		
Parameter name	PCS Low	PCS High
Potassium	≤3 mmol/L	≥6 mmol/L
Chloride	≤90 mmol/L	≥118 mmol/L
Bicarbonate	≤16 mmol/L	≥35 mmol/L
Glucose	≤2.2 mmol/L	≥9.7 mmol/L
Calcium	≤2 mmol/L	≥3 mmol/L
Phosphorus	≤0.6 mmol/L	≥1.7 mmol/L
Albumin	≤25 g/L	≥625 g/L
Total protein	≤45 g/L	≥100 g/L
URINALYSIS		
Glucose	N/A	≥++++
Ketones	N/A	≥++++
Protein	N/A	≥++
ULN = upper limit of normal		

This table is from 221AD301 and 221AD302 study SAPs.

Potential serious hepatotoxicity

Potential serious hepatotoxicity is defined as ALT or AST ≥3x ULN and total bilirubin >2x ULN at any time post-baseline (not necessarily concurrent). A scatterplot of the maximum post-baseline ALT or AST value relative to ULN and maximum post-baseline total bilirubin value relative to ULN (not necessarily concurrent) for each subject will be provided. A line plot of ALT, AST, ALK and total bilirubin values over time for subjects with potential serious hepatotoxicity will be provided. A listing of subjects with potential serious hepatotoxicity will be provided.

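### PCS laboratory analysis: entry depends on an undefined active treatment period, and the albumin PCS High limit as read can never be met (both minor)

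*SAP*

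**What the plan says.** **Entry rule.** SAP 5.7.5.2 summarises how many participants have a PCS laboratory value after baseline, using the limits in Table 8. To be included, a participant needs a baseline value that is not already PCS (a missing baseline is allowed) and must meet this condition: "Subjects need to have at least one post-baseline evaluation in the active treatment period".

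The other rules in the same subsection are worded differently:

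- Shift tables: "Subjects need to have at least one post-baseline evaluation and a baseline value not low or high or positive (including missing").
- Potential serious hepatotoxicity: raised ALT or AST together with "total bilirubin >2x ULN at any time post-baseline (not necessarily concurrent").
- The PCS count itself is of post-baseline abnormalities, with no period limit.

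SAP 3.3 names two periods, core and LTE. For participants with no LTE dose, the "core treatment period is from the first dose in study to the very last date of any assessment done". The LTE period runs from the first LTE dose to the last assessment. SAP 3.1 sets the EOT date at the last dose date.

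**Albumin limit.** Table 8 as read gives albumin PCS Low as 25 g/L or less and PCS High as 625 g/L or more. Total protein PCS High is 100 g/L or more. The note under the table says: "This table is from 221AD301 and 221AD302 study SAPs".

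**Role of the analysis.** SAP Table 10 says that the PCS analysis replaces the CTCAE-grade laboratory summaries planned in the protocol.

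**The concern.** An entry rule fixes the denominator for every parameter in Table 8. If one of its terms is undefined, two programmers can produce different denominators from the same data. The adjacent shift tables, which draw on the same samples, would then rest on a different set of participants. The people at risk of being dropped are early discontinuers, whom a safety table should not lose by accident. Entry and counting would also follow different rules: entry limited to a period, events counted at any time after baseline.

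The albumin cell is a simpler matter. A threshold that no sample can reach yields a row of zeros, which a reader of the study report could take as a finding.

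**Working it through.** **1. When laboratory samples are taken (nominal days)**

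- Protocol Table 1: hematology, chemistry and urinalysis at Screening only.
- Protocol Table 2: Week 52 (Day 365) and Week 102 (Day 714). The Week 100 dose is Day 701.
- Protocol Table 3: Week 154 (Day 1078). The Week 152 dose is Day 1065.
- Protocol Table 5, for those who stop treatment but stay in the study: Week 48 (Day 337), Week 102 and Week 154.

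So the first scheduled on-treatment sample is Day 365, and the first scheduled sample after stopping is Day 337.

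**2. Possible ends of the period**

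- A: the last dose date (the EOT date in SAP 3.1).
- B: the last dose plus 28 days. The exposure formula in SAP 5.5.1 has last dose − first dose + 29 = (last dose − first dose + 1) + 28, which is a 28-day tail.
- C: the core and LTE periods of SAP 3.3, which together run to the last assessment.

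**3. Cases**

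| Case | Last dose | Earliest post-baseline lab | Gap (days) | A | B | C |
|---|---|---|---|---|---|---|
| Stops after Week 8, stays in study | Day 57 | Day 337 | 337 − 57 = 280 | out | out | in |
| Core completer, no LTE, Week 52 lab missing | Day 701 | Day 714 | 714 − 701 = 13 | out | in | in |
| Still dosed at Week 52, lab taken | Day 365 or later | Day 365 | none | in | in | in |

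All three enter the shift tables if the baseline value qualifies. On scheduled samples alone, reading A removes everyone whose last dose came before Week 52. Reading B does nearly the same, except that a last dose at Week 44 (Day 309) just reaches the Week 48 sample: 309 + 28 = 337. An unscheduled sample taken in time would also restore a participant.

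Under reading A the end-of-treatment sample never qualifies for entry. It falls 13 nominal days after the last dose (714 − 701 and 1078 − 1065). SAP Table 2 has the same order: "Week 154/End of Treatment Visit (within 2 weeks of last dose"). This affects only participants with no earlier post-baseline sample.

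**4. Albumin**

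- Against total protein PCS High: 625 / 100 = 6.25.
- Against its own PCS Low: 625 / 25 = 25.
- High/low ratio in the other eight two-sided chemistry rows: sodium 1.24, chloride 1.31, calcium 1.50, potassium 2.00, bicarbonate 2.19, total protein 2.22, phosphorus 2.83, glucose 4.41.
- In the nine two-sided hematology rows the ratio runs from 1.62 (hematocrit, males) to 15 (lymphocytes).

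Albumin is a component of total protein (general knowledge, not stated in the SAP). An albumin of 625 g/L would need a total protein of at least 625 g/L, so the expected count in that cell is 0. If one decimal point was lost, which is an assumption, the ratio would be 62.5 / 25 = 2.5, within the range of the other chemistry rows.

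**The case against.** The best defence of the entry rule is that the SAP already points to the harmless reading. SAP 5.1 bases all analyses on data from the whole study, core and LTE. SAP 5.7.5.2 opens by including all values. SAP 3.3 carries its periods through to the last assessment when dosing has stopped. In a single-arm open-label study the word active excludes nobody. Readings A and B borrow date conventions that the SAP never offers as the end of this period. Most of this stands, and it makes reading C the more coherent one. But under C the five words do nothing, and a qualifier that appears in one rule and is absent from the rule beside it invites the narrower reading. The statement on including all values concerns which records are used, not who enters.

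A reader might go further and say that the rule breaches the treatment-policy strategy of SAP 5.7.1, which applies "regardless of intercurrent events including treatment discontinuation and use of concomitant therapies". The documents do not support that. The variable of that estimand is adverse events. The same section does say "The Safety population will be used for safety analyses of AEs, clinical laboratory data", but naming a population does not rule out an evaluability condition, and the shift tables have one too. At most, an on-treatment limit would be out of step with the approach to safety elsewhere in the SAP.

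On albumin, the text was machine-read and the exponents in Table 8 were flattened, so a lost decimal point is possible. Decimals in nearby cells did survive (10.7, 176.8, 2.2, 9.7, 0.6, 1.7), which makes that less likely but does not exclude it.

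**Conclusion.** Two minor points stand.

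**Entry rule.** The term is undefined, and the PCS denominator depends on how it is read. The effect is zero under the SAP 3.3 periods. Under an on-treatment reading, early discontinuers drop out of the PCS analysis while staying in the shift tables. How many cannot be derived from the documents. A reader might infer that the plan does exclude early discontinuers; the text does not establish that, because the harmless reading is also open.

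**Albumin.** As read, the PCS High limit cannot be met, given that albumin is part of total protein. A reader might infer a proven error in the plan, or that 62.5 g/L was meant. Neither follows without the original page and the source SAPs. Even if 625 is what the plan prints, only one cell is lost: albumin PCS Low, the albumin shift tables and the by-visit albumin summaries still work.

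The SAP plans no statistical testing, and no primary AE, ARIA or ADA endpoint is touched.

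**What to change.** 1. Delete the five words that limit the evaluation to the active treatment period, so that PCS entry matches the shift-table rule. If an on-treatment analysis is intended, define the start and end of the period instead, and apply it both to entry and to the values counted.
2. Check the albumin PCS High cell on the original page and in the 221AD301 and 221AD302 SAPs. If the original also reads 625, correct it from the source or enter N/A.

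The cost is five words and at most one table cell, with the matching program lines. The small downside of the deletion is that some samples taken long after the last dose are counted (280 days in the case above), as the shift tables already do.

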5.7.6. C-SSRS Data

The Columbia Suicide Severity Rating Scale (C-SSRS) is an assessment that evaluates suicidal ideation and behavior.

A summary of post-baseline C-SSRS results will be presented the following information: number of subjects with at least one post-baseline C-SSRS assessment, number of subjects with post-baseline suicidal ideation, number of subjects with post-baseline suicidal behavior, number of subjects with post-baseline suicidal ideation or behavior, and number of subjects with post-baseline non-suicidal self-injurious behavior.

The following listings will be provided:

Study: 221AD304 Version: 2.0

a) Listing of C-SSRS for subjects with post-baseline suicidal ideation, suicidal behavior, or non-suicidal self-injurious behavior

- b) Listing of C-SSRS for subjects with post-baseline suicidal ideation
- c) Listing of C-SSRS for subjects with post-baseline suicidal behavior

5.7.7. ECG Data

The 12-lead electrocardiograms (ECG) data will be summarized using shift table based on subjects with at least one post-baseline ECG assessment and whose baseline ECG assessment was not abnormal. This includes shift from normal or unknown at baseline to abnormal post-baseline, shift from normal or unknown at baseline to not adverse event or abnormal post-baseline, and shift from normal or unknown at baseline to adverse event post-baseline.

The number and percentage of subjects with shifts to abnormal ECG, not adverse events, and subjects with shift to abnormal ECG, adverse events at any time during post-baseline will be summarized.

5.7.8. Vital Sign Data

Vital sign parameters include body temperature, systolic blood pressure, diastolic blood pressure, heart rate, respiration rate and weight. Vital signs will be measured with the subject supine and after the subject has been resting for at least 10 minutes.

Clinically relevant post-baseline abnormalities in vital signs will be presented with criteria defined below:

- $< 36 \, ^{\circ}\text{C} \text{ and} > 38 \, ^{\circ}\text{C} \text{ for body temperature}$
- < 60 bpm and > 100 bpm for pulse
- < 90 mmHg, > 140 mmHg and > 160 mmHg for systolic blood pressure
- < 50 mmHg, > 90 mmHg and > 100 mmHg for diastolic blood pressure
- \geq 7% increase and \geq 7% decrease from baseline in weight
- < 12 breaths/min and > 20 breaths/min for respiratory rate

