- 9. Uncontrolled hypertension defined as: average of 3 SBP/DBP readings > 165 mmHg and/or > 100 mmHg at Screening (blood pressure measurements exceeding these limits may be repeated as warranted by the Investigator, but values must be within the specified limits for the participant to be eligible for the study), or persistent SBP and/or DBP

[figure not shown]
- readings > 180 mmHg and/or >100 mmHg, respectively, 3 months prior to treatment (Day 1) that, in the opinion of the Investigator, are indicative of chronic uncontrolled hypertension.
- 10. History of malignancy or carcinoma. The following exceptions may be made after discussion with the Sponsor:
  - Participants whose cancer is in remission according to the cancer specialist prior to Screening.
  - Participants with a history of excised or treated basal cell or squamous carcinoma of the skin.
- 11. A seizure event that occurred after the last visit of the feeder study and before Screening for this study.
- 12. Evidence of impaired liver function as shown by an abnormal liver function profile at Screening (e.g., repeated values of AST and  $ALT \ge 2 \times the$  upper limit of normal).
- 13. History or evidence of an autoimmune disorder considered clinically significant by the Investigator or requiring chronic use of systemic corticosteroids or other immunosuppressants.
- 14. Recent history (within 1 year of Screening) of alcohol or substance abuse as determined by the Investigator, a positive urine drug (due to nonprescription drug) or alcohol test at Screening or use of cannabinoids (prescription or recreational).
- 15. Clinically significant systemic illness or serious infection (e.g., pneumonia, septicemia) within 30 days prior to or during Screening.
- 16. History of or known seropositivity for HIV.
- 17. Current hepatitis C infection (defined as positive HCV antibody and detectable HCV RNA. Participants with positive HCV antibody and undetectable HCV RNA are eligible to participate in the study (Reference: United States Centers for Disease Control and Prevention).
- 18. Current hepatitis B infection (defined as positive for HBsAg and/or total anti-HBc). Participants with immunity to hepatitis B from previous natural infection (defined as negative HBsAg, positive anti-HBc, and positive anti-HBs) or vaccination (defined as negative HBsAg, negative anti-HBc, and positive anti-HBs) are eligible to participate in the study.

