### 16.4.2.5. Columbia Suicide Severity Rating Scale

The baseline and postbaseline C-SSRS data will be summarized. C-SSRS data will be summarized using descriptive statistics (number of participants, mean, standard deviation, median, minimum, and maximum) for continuous variables, and using frequency and percentage for discrete variables.

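### SAP 5.7.8 counts five vital signs against fixed post-baseline limits whatever the baseline value, so the table cannot separate pre-existing from new abnormality

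*SAP*

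**What the plan says.** SAP 5.7.8 gives the whole vital-sign analysis in one rule: "Clinically relevant post-baseline abnormalities in vital signs will be presented with criteria defined below". The limits include:

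- systolic pressure: "< 90 mmHg, > 140 mmHg and > 160 mmHg for systolic blood pressure"
- diastolic pressure: "< 50 mmHg, > 90 mmHg and > 100 mmHg for diastolic blood pressure"
- pulse: "< 60 bpm and > 100 bpm for pulse"

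Temperature and respiratory rate also have fixed limits. Weight is different: it is flagged at a change of 7% or more from baseline. The section states no baseline condition, denominator or shift table, and it does not say whether counting is by visit or at any time.

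Two neighbouring sections do set a baseline condition. The laboratory analysis of potentially clinically significant (PCS) values requires "a baseline value not potentially clinically significant (including missing) to be included in the analysis", and the laboratory shift analysis has a parallel rule. The ECG table is "based on subjects with at least one post-baseline ECG assessment and whose baseline ECG assessment was not abnormal".

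Protocol 8.2, criterion 9, excludes a participant whose blood pressure shows "average of 3 SBP/DBP readings > 165 mmHg and/or > 100 mmHg at Screening". Values up to those limits are admitted.

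For the suicidality scale, protocol 16.4.2.5 states: "The baseline and postbaseline C-SSRS data will be summarized". SAP 5.7.6 plans post-baseline counts and listings only.

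**The concern.** The vital-sign limits overlap the range in which participants may enrol. Someone with a systolic pressure of 162 mmHg before the first dose and 162 mmHg at a later visit meets both the >140 and the >160 rows, although nothing has changed. That person would look the same in the table as someone who rose from 125 to 162 mmHg.

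The study has one arm and no planned testing (SAP 5.1), so the participant's own baseline is the natural reference for these tables. If the baseline is neither built into the count nor shown beside it, the reader cannot judge how much of a percentage arose on treatment. C-SSRS raises a smaller version of the same question: post-baseline ideation is counted without showing how many participants reported it at entry.

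**Working it through.** The plan states no expected abnormality rate, so there is no figure to reproduce. The check compares the rules, then illustrates the possible size.

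**1. Baseline conditions in the SAP**

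| Analysis | Section | Baseline-abnormal participants left out? |
|---|---|---|
| Laboratory shift | 5.7.5.2 | Yes (missing baseline kept) |
| Laboratory PCS | 5.7.5.2 | Yes (missing baseline kept) |
| ECG shift | 5.7.7 | Yes (unknown baseline kept) |
| Potential serious hepatotoxicity | 5.7.5.2 | No |
| Weight | 5.7.8 | Not needed; criterion is a change |
| Temperature, pulse, SBP, DBP, respiratory rate | 5.7.8 | No |
| C-SSRS | 5.7.6 | No |

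SAP 3.1 defines baseline, but neither 3.1 nor 5.7.1 supplies a general baseline rule for vital signs.

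**2. Can the reader recover the baseline elsewhere?** The demographic summary in SAP 5.3 includes height, weight and BMI. Its visible text has no blood pressure, pulse, temperature or respiratory rate. SAP 5.7.8 plans no change-from-baseline summary except for weight.

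**3. Where eligibility lets carry-over in**

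- SBP >140: screening values from 141 to 165 mmHg are admitted.
- SBP >160: only 161 to 165 mmHg, a narrow band.
- DBP >90: 91 to 100 mmHg is admitted.
- DBP >100: a screening average above 100 is exclusionary, so carry-over should be small. It is not zero, because baseline is the last pre-dose value rather than the screening average.
- Pulse <60: no visible criterion excludes a low resting pulse as such.

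**4. Number of readings** (protocol Tables 1 to 3). Weeks 4-48 give 12, Weeks 52-100 give 13, and Week 102 gives 1: 12 + 13 + 1 = 26. A core-only completer adds the follow-up visit: 27. A full LTE participant adds 13 dosing visits, Week 154 and Week 170: 26 + 15 = 41. Early termination means many LTE participants will have fewer.

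**5. Chance that a baseline abnormality is counted.** Assume that any single reading counts, and that the abnormality recurs independently at each visit with probability q. Then P = 1 − (1 − q)^k.

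- Vital signs, k = 26: q = 0.1 gives 1 − 0.9^26 = 93.5%; q = 0.3 gives 99.99%.
- C-SSRS, k = 3 (Weeks 50, 102 and 154): q = 0.1 gives 1 − 0.9^3 = 27.1%; q = 0.5 gives 1 − 0.5^3 = 87.5%.

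**6. Illustration for SBP.** None of these inputs is in the documents. Person means are normal with mean 125-135 mmHg. The between-person and within-person SDs are 12 and 8, or 14 and 10. The screening average of three readings is capped at 165. There is one baseline reading and 26 post-baseline readings.

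| Mean / SDs | >140: counted | of these, >140 at baseline | counted among those not >140 at baseline | >160: counted | of these, >160 at baseline |
|---|---|---|---|---|---|
| 125 / 12, 8 | 52.5% | 27.4% | 44.7% | 6.5% | 9.1% |
| 130 / 12, 8 | 67.4% | 35.2% | 57.5% | 12.9% | 11.1% |
| 135 / 12, 8 | 80.3% | 44.2% | 69.7% | 22.9% | 14.0% |
| 135 / 14, 10 | 83.6% | 43.9% | 74.4% | 34.5% | 15.6% |

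The carry-over share is (proportion abnormal at baseline × proportion of those counted later) ÷ proportion counted. For the second row: 0.241 × 0.984 ÷ 0.674 = 0.352.

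**7. Does a baseline condition remove dependence on visit number?** No. With mean 130 and SDs 11 and 9, the proportion above 140 goes from 74.4% at 27 visits to 78.7% at 41 without the condition (4.3 points). With the condition it goes from 67.1% to 72.5% (5.4 points).

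**The case against.** The SAP does what the protocol asked. Protocol 16.4.2.3 says only that vital-sign analysis will concentrate on clinically relevant abnormalities, while 16.4.2.2 and 16.4.2.4 ask for shifts in laboratory and ECG data. SAP Table 11 attributes the vital-sign criteria to a sponsor standard. New hypertension or bradycardia reported as an adverse event still passes through the treatment-emergent rule, which covers worsening. These are supporting descriptive tables in an abbreviated report. All of this stands. It limits the importance of the point, but it does not supply the missing baseline information.

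A reader might go further in several ways that the documents do not support:

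- **That emergent abnormality is the table's only purpose.** The protocol does not say so.
- **That every vital sign is affected, or that all laboratory analyses condition on baseline.** Weight is already baseline-referenced, and the hepatotoxicity rule has no baseline condition.
- **That excluding baseline-abnormal participants has no drawback.** A participant at 162 mmHg who rises to 200 would then leave both systolic rows.
- **That the same change would stop longer follow-up from raising the counts.** Step 7 shows that it would not. Adverse-event incidence proportions share that property.
- **That pre-existing suicidal ideation cannot be identified at all.** SAP 5.7.6 plans listings for every participant with a post-baseline finding, and does not state that they are limited to post-baseline records. With three scheduled post-baseline assessments (a fourth under the revised follow-up in SAP Table 2), accumulation is limited. Whether dropping the baseline summary was declared cannot be settled, because one row of SAP Table 10 is not readable.

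**Conclusion.** The point holds for temperature, pulse, SBP, DBP and respiratory rate. As written, SAP 5.7.8 mixes abnormality present at entry with abnormality that appeared later, and no other planned summary separates them. Carry-over is likely to matter most at SBP >140, DBP >90 and pulse <60. It should be smaller at SBP >160 and small at DBP >100.

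The actual size is not known from the documents. The 27-44% (SBP >140) and 9-16% (SBP >160) shares rest on assumed blood-pressure distributions, full attendance and counting of any single post-baseline reading. They show the order of size that is possible and are not estimates for this trial.

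The C-SSRS part is weaker but real: the SAP omits a baseline summary that the protocol promises. No test, sample size or primary safety parameter is affected. The change is worth making because it costs little.

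**What to change.** In SAP 5.7.8, keep the existing rows and state whether they count any post-baseline reading or are by visit. For the five parameters other than weight, add one of the following:

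- a shift table from baseline category to worst post-baseline category; or
- the number meeting each criterion at 221AD304 baseline, plus the incidence among participants not meeting that criterion at baseline (missing baseline included, as in the laboratory PCS rule).

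Keeping the existing rows retains post-baseline values in participants already abnormal at entry. The shift table also shows movement from one category to a worse one, so it is slightly preferable.

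In SAP 5.7.6, restore the baseline C-SSRS summary and add the number of participants with post-baseline ideation or behaviour not present at baseline.

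Vital signs and C-SSRS are already collected before the first dose, so no new data are needed. The cost is a little programming and table space. Dependence on the number of visits remains and could be noted in a footnote.
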